5.13.5.1. Quality Control

Biorep will analyse incoming samples for quality. Plasma will be analysed for haemoglobin contamination due to haemolysis using a HemoCue plasma Haemoglogin analyser. Creatine phosphokinase, lactate dehydrogenase and C-reactive protein levels will be measured spectrophotometrically as markers of plasma protein integrity. Periodically samples will also be assessed by [name] (Imperial College) using NMR analysis.

5.13.6. QA/QC systems for cognitive assessment

Quality Assurance

Training – Cognitive Examiners must be trained at a face to face, or webinar training session and certified by an approved cognitive trainer prior to running any participants. Prior to face to face training, the trainee should review the operating procedures manual.

During the training, the following occurs:

- · Trainer instructs trainees on optimizing participant test performance
- · Trainer instructs trainees on importance of and methods for standardized administration
- Trainer orients trainees to the test battery
- Trainer demonstrates test battery administration
- · Trainees practice full test battery administration on each other with informal feedback from trainer
- Trainee administers full test battery to trainer
- Trainer provides written feedback to trainee and either
 - Certifies the trainee to test participants with the caveat that the initial administration must be videotaped and sent in for evaluation, OR
 - Requires trainee to do additional work, including
 - o practice at the home site to address shortcomings highlighted in the written training session feedback
 - o video recording of a practice administration of the test battery
 - o Certification based on the trainer's rating of the videotaped practice administration

This training and certification process is executed each time the test battery is changed in any way that alters the test battery administration. In addition to initial certification, cognitive examiners may be required to submit a videotape of at least one test administration per year e.g. new rater. This tape is reviewed by a cognitive trainer and written feedback is provided to the examiner. In some cases, corrective action will be required and the trainer may request a second videotape of a battery administration that demonstrates the cognitive examiner has addressed the trainer's concerns.

Equipment - Standard operating procedures require calibration all relevant hardware before each administration. The touch surface of the tablet PC needs to be calibrated to increase precision of spatial measurements. Document scanners require setup to be done consistently to maintain quality of scanning from site to site. For audio recordings, the hardware and the software need to be setup properly to ensure a useful recording in every circumstance.

Quality Control

All paper/pencil tasks will be scored by the examiner at the home site and then rescored by a certified scorer. Discrepancies will require a third scoring. A cognitive trainer will provide feedback to the examiners who produce score that are consistently discrepant from those of the secondary and tertiary scorers.

Electronic Data Collection Quality Control – Data generated by electronic means must be collected, recorded and reported, as consistently, accurately and precisely as possible.

- Collection refers to the administration of the tasks by cognitive examiners.
 - Collection must be done in a consistent and reliable way such that the data are not affected by individualized administration practices.
 - Cognitive examiners will be trained on proper administration of the tasks to reduce collection errors as much as possible.
- Recording refers to the dependent variables of the computerized task, such as response time, or inter-tapinterval variance.
 - As the tasks are written, each program undergoes a strict QA process to verify that the program
 is measuring what it claims to measure within the required specifications and this reduces
 recording errors. All data measured by the tasks must be as accurate and precise as possible for
 all hardware.
- Reporting refers to the association of data with the correct administration in the database.
 - Each participant number from each site for each visit must be correctly linked to the proper and complete set of administration data for the tasks. Time and date stamps are taken for each task administration, and additionally participant number, site and visit numbers are all recorded for each battery administration. This information, along with notes about the administration from the cognitive examiner, are used to link the electronically collected data to the official list of administrations. This reduces reporting errors.

5.13.7. OA/OC systems for quantified motor assessment

Quality Assurance

Validation of the hardware and software – All equipment will be assembled and tested at the laboratory of [name] in Muenster and shipped to the study sites. After the equipment is installed at individual sites, 1-2 mock participants will be assessed using the complete protocol. These data will then be sent to [name] for inspection to ensure that the equipment has been correctly installed at the sites, is working, and is producing usable and accurate data.

Calibration of equipment

The force transducer, force-plate, and Polhemus 3D-position-sensor used for the assessments are industrial standard pre-calibrated systems at factory delivery and do not require recalibration. They are used in robotics in industrial processing and calibration is assured by electronic circuits including adjustments for temperature.

Training, certification, and re-certification of examiners

Revised: 2nd September 2013 68 Version 5.2

All examiners must be trained in a face-to-face setting by a certified trainer. As part of the training, the trainer will observe the examiner administering the tasks, provide written feedback to the examiner regarding the administration of each of the tasks, and, when the examiner is considered to have the skills for standard task administration, the trainer will add the examiner to the list of certified Track-HD quantitative motor examiners. Re-certification is required on an annual basis and can be accomplished either in person or by videotapes available via the EHDN motor training website (again, reviewed by a certified trainer for approval of recertification). In addition, videotaped sample assessments of all paradigms used will be made available on the EHDN website.

Quality Control

Data Quality will be monitored by [name] and colleagues in Muenster by conducting intensive review of the data from 1-2 mock participants at each site before the start of the study, and then by reviewing data from participants from all sites within four weeks of delivery. Specifically, this data review will include an inspection of the data for completeness, and range to check for range violations. Any anomalies found in the data will be followed up by either further training at the sites or checking and repair of the equipment as necessary.

5.13.8. QA/QC systems for imaging assessment

Quality Assurance

The Imaging CRO will put in place QA procedures to ensure that scans obtained at different times in different centres using different hardware/software combinations are as comparable as possible. This will include standardisation of scanning protocols and inter-scanner comparisons using phantoms or human volunteers. The Image Acquisition preparatory phase work for Track-HD was led by [name], and [name] and IXICO Ltd for Visits 5 and 6, and [name] for visit 7.

Quality Control

The local site PI is responsible for ensuring clinical assessment of the scans by a local radiologist within five working days of the scan and will be responsible for clinical follow-up if any abnormalities detected.

Imaging QC and feedback to sites will ultimately be carried out centrally by the Imaging CRO. This is detailed in the Imaging Track-HD SOP document.

5.13.9. QA/QC systems Transcranial Magnetic Stimulation (TMS)

Quality Assurance

TMS stimulators, associated equipment and settings will be standardised between sites. All sites will use MagStim 200 stimulators, or newer, and figure-of-eight coils with 90mm outer winding diameter with posterior to anterior current flow. Data acquisition will follow a standard protocol provided by [name] on behalf of the TMS advisory group. Other QA procedures will include a standard operating procedure for TMS and a check-list to ensure that equipment and software settings, and data recording, follow the TMS protocol. Performance of each TMS lab and inter-investigator variability will be assessed by [name] with at least one human volunteer being tested at all sites before data collection begins. All preparatory work for TMS is being led by [name] on behalf of the TRACK-HD TMS advisory committee.

Quality Control

All TMS data uploaded onto the TRACK-HD data repository will be monitored within a week by [name] and his team. Data will be examined for completeness, for any potential data entry errors and for potential

equipment problems. Any query will be fed back to the site to ensure acquisition of data is of the best possible quality.

5.13.10. QA/QC systems for oculomotor assessment

Quality Assurance

All testing sites will be provided with a Saccadometer and experimenters will be trained and assessed in the administration of the oculomotor test battery. All oculomotor examiners must be trained at a face to face training session, and certified by an approved oculomotor trainer prior to running with any participants. Prior to face to face training, the trainee should review the operating procedures manual. During the face to face training:

- 1. Trainer instructs trainees on optimizing participant test performance
- 2. Trainer instructs trainees on importance of and methods for standardized administration
- 3. Trainer orients trainees to the test battery.
- 4. Trainer demonstrates test battery administration
- 5. Trainees practice full test battery administration on each other with feeback from the trainer
- 6. Trainer certifies the trainee to test participants with the caveat that the initial administration must be videotaped and sent for evaluation

The major elements of the oculomotor test battery are easily visible at a distance and the quality of the data can be assessed via the CTMS. A physical trip a clinical site will be undertaken if significant problems are revealed in the video recordings, or if sites experience systematic problems.

Quality Control

Once the oculomotor test battery is running as planned, QC becomes focussed on data management. The primary QC will be weekly checks via the CTMS to ensure that the data is being stored correctly. This will be assessed in the following ways:

- 1. Light levels will be regularly monitored in the testing environment and reported on a monthly basis to ensure they remain within the specified boundaries for the LCSLC
- 2. The number of data files added to the database per week will be compared with the expected amount.
- 3. Data files for that week will be downloaded and checked to ensure that they can be opened with the program LatencyMeter (Ober Consulting), that the Clinic, Experimenter and Participant IDs are all entered correctly, and that the data itself fits the expected profile.

5.14. General statistical principles for TRACK-HD

5.14.1. Underlying assumptions: relationship between TRACK-HD study design & goals

To quote section 4.8: The primary aim of the study - to provide essential methodological advances needed for optimizing neuroprotective clinical trials in HD - has already yielded a range of quantitative outcome measures suitable for use in potential clinical trials in the early stages of the disease. Track-HD will now focus on individual and combined clinical and biological outcome measures for tracking progression in the premanifest stages of the disease, in which despite significant progressive regional and whole-brain atrophy and clear cross-sectional deficits compared with controls, there has so far been limited detectable cognitive or motor decline (Tabrizi et al. 2011).

A number of assumptions are implicit in the marriage of this objective to the study design of Track-HD. We here attempt to make these assumptions explicit with the goal of clearly linking the planned data analysis to the study objective.

Longitudinal changes in the outcome measures (candidate markers) are the primary objective of study.

For the premanifest group, naturalistic observation of longitudinal change mimics the course expected of future clinical trial participants receiving either a placebo or a completely ineffective treatment. This assumption seems logical such that it can be made with some confidence. (However, it does not allow for the possibility of true placebo effects in future trials.)

For the non-expanded control group, longitudinal change mimics the course that would be expected in a completely effective treatment of HD under the additional assumption that the characteristic in question is a valid surrogate outcome. This assumption is clearly less certain. For example, it is conceivable that a completely effective treatment could either lead to reversal of previous HD-induced change or fail to immediately arrest the "momentum" built into longitudinal changes that are occurring at the time effective treatment is introduced. Nonetheless, for study planning, sample size estimation, etc. it seems difficult to preferentially choose and quantify either of these alternatives.

Change that is observed in the control group will reflect a number of other phenomena associated with longitudinal observation: (a) imperfect measurement reliability (b) short-term within-participant fluctuation in the true phenomenon being measured—which, along with (a) leads to regression towards the mean)—(c) background long-term causative effects such as aging, and (d) practice effects. These phenomena are also assumed present in the CAG-expanded groups, along with the potential longitudinal effect of evolving HD.

Given the prior assumptions, the differences in longitudinal marker change between the premanifest group and the control group are estimates of the maximum possible surrogate treatment effect achievable via that marker in a clinical trial. Since hypothesized treatment effects will typically be considerably less than 100%, these longitudinal differences will need to be notable if the marker is to pass this criterion for candidate surrogacy.

None of the above is meant to distract from the other considerable hurdles that a marker must overcome in order to reach surrogate-outcome status.

Even markers that do not qualify as surrogate outcomes can be quite valuable as risk stratifiers. It can be shown that various strategies related to stratification in recruitment and/or analysis lead to substantial improvement in the power of clinical trials. Thus we do not underestimate the importance of a secondary goal of the study, cross-sectional comparison of groups on the basis of candidate markers.

5.14.2. General principles of statistical analysis

We will strive to always distinguish between a priori and post hoc hypotheses, with a priori hypotheses defined as comprehensively as possible before data analysis begins. An honest distinction is critical to true progress and optimal allocation of future resources in HD research, since the nominal statistical significance for a post-hoc hypothesis, suggested only by preliminary exploration of the data, is typically inflated in ways that are often impossible to quantify (Good & Hardin, 2006).

We will rely on mixed effect linear models to assess most longitudinal change (Verbeke & Molenberghs, 2000; Littell et al., 2006). Fixed effects will typically include group (diagnosed, premanifest, or control), age, gender, time-since-first-measurement ("time", which will be 0 at baseline), and interactions between group and time. Substantial interactions between group and time will usually be the main parameters of interest. Other fixed covariates will be determined by anticipated confounders for the specific outcomes. For example, most psychometric tests require adjustment for years of education.

Depending on the year of enrolment and study visit at which an assessment was introduced for the first time, the number of existing measurements for each TRACK-HD assessment will range from 2 to 4 measurements over 1 to 3 years. Additional data collected for these assessments will contribute to the overall ongoing longitudinal analyses. For new assessments, e.g. fRMI, and TMS, and/or new participants there will be 3 measurements over 2 years; and Viritual Maze task, Go-No-Go task, VEPs, TMS-EEG, CEST, NODDI and MTR there will be cross-sectional data only.

Our primary hypotheses will treat time as a linear effect unless there is a compelling a priori reason to use varying degrees of freedom in estimating separate effects for specific participants and/or assessments. Secondary analyses will typically explore whether longitudinal change is related to estimated prognosis within the premanifest group (based on CAG and age). Random effects will always include a within-participant term. Our sample size will be such that we will generally model unstructured within-participant covariance over visits. Other candidate random effects will include variance components for study site and examiner, as appropriate.

Certain longitudinal outcomes will not be amendable to the methods described above in 2. Categorical outcomes or counts will instead be modelled using mixed generalized linear models (e.g. logistic, Poisson), with other considerations identical to those above (Agresti, 2002; Littell et al., 2006). Conversions of status (i.e., diagnosis) will be analyzed by survival analysis. Multivariate-outcome imaging data present special longitudinal challenges. Changes over a single time interval can usually be approached using methods designed primarily for cross-sectional analysis. (The one set of changes is the single "cross-sectional" measurement.) In other instances, the multivariate data are reducible to one or a few summary statistics that can be handled by standard longitudinal methods. These limited generalizations notwithstanding, analysis plans for the imaging component will be described separately below.

Cross-sectional analyses will typically be by linear model with the fixed effects described in 2 above as the predictor variables. Scientific interest will generally focus on group effects between controls and premanifest.

Longitudinal studies inevitably entail loss to follow-up. We will monitor drop-out rates and, prior to final analyses, we will investigate whether probability of drop out is predictable on the basis of information known about the participants, including research data acquired at previous visits. If there is notable drop-out, that appears unpredictable ("completely at random" in statistical parlance), and there is no basis for suspecting that it is related to outcomes of interest, then we will proceed with the previously described methods without modification. For our analyses using mixed modelling theory, we will proceed if the data missingness appears predictable based on known data regarding the participants ("missing at random" but not "missing completely at random"), as these methods handle such missing data appropriately. In other analyses with substantial, plausibly "missing-at-random" data, we will employ multiple imputation methods to assess the effect of such drop-out on our analyses. If there is substantial drop-out and strong reason to think that it is not missing at random, then our analyses will be subject to sensitivity analyses across a range of assumptions regarding the relationship between drop-out and outcomes. All principles and procedures mentioned in this paragraph are reviewed in greater detail by Verbeke and Molenberghs (2000) and Molenberghs and Kenward (2007).

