4.9. Study population

At the start of TRACK-HD, clinical trials in HD were uncommon and lacked the appropriate outcome measures. However, a number of candidate therapeutics with potential disease-modifying effects are currently being tested in early stage disease and it is therefore appropriate that eligible individuals in TRACK-HD be offered the opportunity to participate in these trials, rather than continue observation in our study. For this reason, early stage participants were not included at TRACK-HD visits 5, 6 and 7. Any early-HD participant who has developed advanced symptoms of HD and is not eligible for clinical trials or further participation in TRACK-HD, will be offered participation in other observational studies such as Registry. Although some of the original PM participants may also have advanced to early stage disease, this cannot be disclosed as part of a research study and therefore these individuals cannot be offered participation in a clinical study for early stage disease, unless clinical onset has been confirmed by their doctor. In these cases, the PM participant may also be invited to take part in a clinical trial. However, if they are unaware of their current disease status, they will be allowed to continue in TRACK-HD.

Each centre initially recruited 90 participants drawn from the population of its HD clinical service, including 30 control participants, 30 premanifest HD expansion carriers (PM) and 30 participants with early disease (stage 1 or 2). Additionally, new premanifest participants were recruited during the third year of the study to replace withdrawn participants. A further 33 controls and 30 PM participants were recruited across sites at visit 5 to replace withdrawals and maintain the statistical power of the study.

In order to increase the yield of disease-related changes in the premanifest cohort, a burden of pathology selection criterion is used. Burden of pathology severity is given by (CAG-35.5) × age. A threshold of >250 CAG-years will be set, which approximates to 15 years to estimated onset (calculations based on Predict-HD dataset by [name]).

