5.8.3. Exclusion criteria

Revised: 2nd September 2013 59 Version 5.2

- Stage 1 (UHDRS diagnostic confidence score of 4) or greater at time of enrolment, unless previously enrolled as a premanifest participant in TRACK-HD
- 2. Less than 18 years of age
- 3. More than 65 years of age (unless previously enrolled in TRACK-HD)
- 4. Major psychiatric disorder at time of enrolment
- 5. Concomitant significant neurological disorder
- 6. Concomitant significant medical illness
- 7. Unsuitability for MRI, e.g. claustrophobia, metal implants
- 8. Unwillingness to donate blood
- 9. History of significant head injury
- 10. Predictable non-compliance by drug and/or alcohol abuse
- 11. Significant hand injuries that preclude either writing or rapid computerized responding
- 12. Participant in Predict-HD
- 13. Currently participating in a clinical drug trial

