5.12.6. Withdrawal from participation

If a participant does not want to continue, the participant can leave the study at any time. Participants do not have to disclose their reasons for withdrawal of consent. On the participant's request, all information obtained so far will be anonymised (identifying data discarded). Similarly, on the participant's request, all biosamples collected and stored at the central Biorep repository may be destroyed. However, samples that have already been distributed for the purposes of HD research cannot be destroyed. Participants have to be aware that an 'End of Study form' must be completed by the investigator, detailing the reasons for withdrawal (e.g. marking "participant request").

Participants may be withdrawn from the study for the following reasons:

- 1. Failure to complete the required study procedures, regardless of reason.
- 2. The site investigator feels that it is in the best interest of the participant.

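### Mixed models may proceed whenever known data predict drop-out, with no condition that those predictors be in the model, so the PM-control slope difference may be biased

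*Protocol*

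**What the plan says.** Section 5.14.2 of the Protocol will examine, before final analysis, whether drop-out can be predicted "on the basis of information known about the participants, including research data acquired at previous visits". For analyses based on mixed-model theory it then says "we will proceed if the data missingness appears predictable based on known data regarding the participants", which it labels missing at random, and gives as the reason "as these methods handle such missing data appropriately".

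The same section describes the model: "Fixed effects will typically include group (diagnosed, premanifest, or control), age, gender, time-since-first-measurement", and the interaction of group with time. It adds that "Other fixed covariates will be determined by anticipated confounders for the specific outcomes". Within-participant covariance is generally unstructured over visits. Prognosis based on CAG and age belongs to secondary analyses.

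Two other remedies appear. Multiple imputation is assigned to analyses other than mixed models. Sensitivity analyses over a range of assumptions are required only when drop-out is substantial and there is strong reason to believe it is not at random.

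**The concern.** The text treats two conditions as one. Being predictable from something the study has recorded is not the condition that a likelihood-based mixed model needs. The model needs missingness to depend only on what is in that model: its covariates and the observed values of that same outcome. A predictor from another domain satisfies the protocol's test but not the model's requirement.

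The slope difference between PM participants and controls is the study's main product. Section 5.14.1 reads it as the largest treatment effect a marker could show, and section 5.15.1 uses it to size future trials and to compare measures. A bias that differs between outcomes, according to how closely each follows the variable behind drop-out, would carry into both uses.

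**Working it through.** **1. The plan's own drop-out figure.** Section 5.16 starts from about 123 PM participants and 102 controls and assumes 10% loss in each group.

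- PM: 123 × (1 − 0.10) = 110.7; the protocol gives 110.
- Controls: 102 × (1 − 0.10) = 91.8; the protocol gives 92.

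These agree apart from rounding. The protocol gives no figure for bias.

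**2. The condition.** Let Y be the outcome, X the model's covariates, Z an observed variable outside the model, and R the drop-out indicator. The mixed model may ignore drop-out if P(R | Y, X) depends on Y only through its observed part. If Z drives drop-out, then P(R | Y, X) = ∫ P(R | Z) f(Z | Y, X) dZ. This depends on the unobserved part of Y unless Z is unrelated to that part given X and the observed Y. So an omitted predictor is harmless only if it carries no further information about the missing values.

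**3. The two lists in section 5.14.2.** The search for predictors covers all known information, including research data from earlier visits in any domain. The model holds group, age, gender, time and group-by-time, plus the outcome's own history through the covariance matrix and any outcome-specific confounders. No rule moves a drop-out predictor from the first list to the second.

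**4. Size, by simulation.** The assumptions, none from the protocol, are:

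- true extra PM decline of 0.100 per year;
- intercept SD 1, slope SD 0.15, residual SD 0.4;
- drop-out in PM participants only, with log-odds 1.5 per SD of the driver;
- 100,000 participants per group and annual visits;
- a model with group, time, group-by-time and unstructured covariance.

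Bias is the group-by-time estimate with drop-out minus the estimate from complete data. A positive value means that decline is underestimated. Dividing by 0.100 gives the share of the decline.

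Drop-out driven by an omitted variable, worse-off participants leaving, by correlation of that variable with the outcome slope:

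| Visits | PM loss | 0 | 0.3 | 0.6 | 0.9 |
|---|---|---|---|---|---|
| 3 | 10% | −0.0005 | 0.0050 | 0.0091 | 0.0129 |
| 7 | 10% | −0.0001 | 0.0027 | 0.0049 | 0.0067 |
| 3 | 30% | 0.0000 | 0.0138 | 0.0264 | 0.0351 |
| 7 | 30% | 0.0001 | 0.0083 | 0.0163 | 0.0215 |

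At 10% loss, correlations of 0.3 to 0.9 give 0.0027/0.100 = 2.7% to 0.0129/0.100 = 12.9%, or about 3-13%.

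- **Drop-out driven by the outcome's own last value:** bias at most 0.0006 in size. Here the protocol's reasoning is right.
- **Better-off participants leaving:** similar size, opposite sign. At 10% loss it is −0.0032 to −0.0128, and at 30% it is −0.0107 to −0.0353.

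**5. Does the remedy work?** Three visits, PM loss of 21-22%, worse-off participants leaving:

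| Correlation | Planned model | Joint model with the auxiliary |
|---|---|---|
| 0.3 | 0.0090 (9%) | −0.0006 |
| 0.6 | 0.0172 (17%) | −0.0011 |
| 0.9 | 0.0250 (25%) | −0.0003 |

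**The case against.** **The model is not closed.** The listed fixed effects are only typical ones. Section 5.15.2 lets investigators add demographic and clinical confounders, and section 5.15.4 tests neuropsychiatric scores as confounders. The wording about proceeding without modification belongs to the completely-at-random case, so a reader who infers that every model must be run unchanged goes beyond the text. This stands. However, these provisions select confounders of an outcome, not predictors of drop-out, and nothing connects the two.

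**Detail may sit in a SAP.** The list of auxiliary variables reasonably could. The decision rule and its justification are in the protocol, and the justification omits its condition.

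**A sensitivity route exists.** Strictly, drop-out driven by a variable outside the model is not at random for that model, so the sensitivity clause could apply. But the protocol labels predictable drop-out as missing at random, which directs the analyst away from that clause.

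**Direction.** A reader might infer that PM decline will be underestimated because the fastest progressors leave first. There is a possible route: where a doctor has confirmed onset, section 4.9 says "In these cases, the PM participant may also be invited to take part in a clinical trial", and section 5.8.3 lists "Currently participating in a clinical drug trial". But the invitation is optional and limited to confirmed onset. Sections 4.9, 5.8.3 and 5.8.4 let progressing PM participants stay, and drug-trial participation is not among the withdrawal reasons in section 5.12.6. Underestimation is plausible but not established.

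**Withdrawal.** A reader might also want to rewrite the ground "Failure to complete the required study procedures, regardless of reason" in section 5.12.6. That ground is permissive, and section 5.12.3 already provides for stopping single tasks. It is a separate matter from the analysis rule.

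**Conclusion.** The point holds as a defect in a stated rule. Section 5.14.2 lets mixed models proceed on a condition weaker than the one they need, so the PM slope and the PM-control difference may be biased. The bias is towards no decline if faster progressors leave for reasons outside the model, and the sign reverses if better-off participants leave. There is none if drop-out follows the outcome's own history or a variable unrelated to it.

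On the assumptions above, with worse-off participants leaving and correlations of 0.3 to 0.9, the bias is about 3-13% of the decline at 10% PM loss, and 9-25% at 21-22% PM loss over three visits. The 10% is the protocol's forward assumption. Larger losses are not far-fetched: section 5.6.4 reports 30 new PM participants at visit 5 against a target of 4 × 30 = 120, or 25% of places. That counts replacements accumulated over time and is not a drop-out rate for the extension.

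The documents do not support a stated direction, or a figure for how far future sample sizes would be inflated, because they give neither the drop-out pattern nor the correlations that such a figure needs.

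**What to change.** Amend the loss-to-follow-up paragraph of section 5.14.2 along these lines:

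- The mixed model stands alone only when drop-out is explained by that outcome's own observed history or by covariates in its model.
- When variables outside the model predict drop-out, the outcome is fitted jointly with those variables, or after multiple imputation that uses them as auxiliaries. Candidates are UHDRS motor score, diagnostic confidence, TFC and CAG-age.
- These variables are not entered as time-varying covariates, because adjusting for, say, current motor score would change the slope being estimated.
- The unadjusted mixed model is reported alongside.

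CAG-age can serve only within the PM group, since section 5.8.2 leaves newly recruited partner controls without CAG testing. Either remedy deals only with drop-out related to recorded values; the existing not-at-random sensitivity clause should stay for the rest.

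The cost is a change of wording and modest programming. The auxiliaries are already collected: Table 10 schedules the UHDRS motor examination and TFC at each of visits 5 to 7, and CAG length is held for PM participants.
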